5 STUDY DESIGN

5.1 Study description

PS0011 is a multicenter, 48-week, double-blind, placebo-controlled, parallel-group, extension study to assess the long-term safety, tolerability, and efficacy of bimekizumab in eligible adult subjects with moderate to severe chronic plaque psoriasis who complete PS0010. At Week 12 of PS0010, all eligible subjects continuing into PS0011 will undergo the PS0010 Week 12 study assessments and any additional PS0011 Baseline assessments, and will then receive their first dose of bimekizumab or placebo in PS0011.

During the Treatment Period, subjects will attend study visits at the study site Q4W for study assessments and administration of bimekizumab or placebo by study site staff through Week 48. Any subject who does not achieve PASI75 response at Week 12 or later in PS0011 will be withdrawn from study treatment and will return to complete the Early Withdrawal Visit assessments. Following completion or early withdrawal from the 48-week Treatment Period, subjects will return for a SFU Visit 20 weeks after their last dose of bimekizumab or placebo in PS0011.

Subjects withdrawing early from the study will undergo the Early Withdrawal Visit assessments and will enter the SFU Period.

Subjects who received placebo or bimekizumab 64mg, 160mg, or 320mg loading dose + 160mg Q4W in PS0010 must achieve PASI90 response at Week 12 in PS0010 to enter the PS0011 extension study on the same treatment dose. Subjects who do not achieve PASI90 response at Week 12 in PS0010 while receiving placebo or bimekizumab 64mg Q4W will be assigned to receive bimekizumab 160mg Q4W on entering PS0011. Subjects who do not achieve PASI90 response at Week 12 in PS0010 while receiving bimekizumab 160mg or 320mg loading dose + 160mg Q4W will be assigned to receive bimekizumab 320mg Q4W on entering PS0011. Subjects who receive bimekizumab 320mg or 480mg Q4W in PS0010 will be assigned to receive bimekizumab 320mg Q4W on entering PS0011, regardless of their PASI90 response at Week 12 in PS0010.

A schedule of study assessments is presented in [Table 5–1](#).

A study schematic diagram of PS0011 is presented in [Figure 5–1](#).

5.1.1 Study duration per subject

The study duration for each subject is estimated to be up to a maximum of 64 weeks:

- Treatment Period: up to 48 weeks
- SFU Visit: 20 weeks after the last dose of bimekizumab or placebo

The end of the study is defined as the date of the last visit of the last subject in the study.

5.1.2 Planned number of subjects and sites

Up to 240 subjects are anticipated to enroll in PS0011 at approximately 40 sites.

5.1.3 Anticipated regions and countries

The regions planned for study conduct are Europe, Canada, and the US, with possible extension to other regions and countries as required in PS0010.

5.2 Schedule of study assessments

A schedule of study assessments is presented in [Table 5–1](#).

REDACTED COPY
This document cannot be used to support any marketing authorization application and any extensions or variations thereof.

Table 5–1: Schedule of study assessments

Protocol activity	Visit Week ^a	Treatment Period													SFU ^b
	PS0011 Baseline	Wk 4	Wk 8	Wk 12	Wk 16	Wk 20	Wk 24	Wk 28	Wk 32	Wk 36	Wk 40	Wk 44	Wk 48/WD		
Informed consent	X ^c														
Inclusion/exclusion	X ^d														
Physical exam ^e	X ^f												X	X	
Body weight	X ^f												X	X	
Vital signs ^g	X ^f	X	X	X	X	X	X	X	X	X	X	X	X	X	
Hematology/biochemistry	X ^f	X	X	X	X	X	X	X	X	X	X	X	X	X	
Urinalysis	X ^f			X			X			X			X	X	
12-lead ECG	X ^f						X						X	X	
Pregnancy testing ^h	X ^f	X	X	X	X	X	X	X	X	X	X	X	X	X	
eC-SSRS	X ^f	X	X	X	X	X	X	X	X	X	X	X	X	X	
IGRA TB test ⁱ	j												X		
TB questionnaire	X ^f			X			X			X			X		
Blood sample for bimekizumab plasma concentrations ^k	X ^f	X	X	X	X			X			X		X	X	
Blood sample for anti-bimekizumab antibodies ^k	X ^f	X	X	X	X			X			X		X	X	
PASI	X ^f	X	X	X	X	X	X	X	X	X	X	X	X	X	
IGA	X ^f	X	X	X	X	X	X	X	X	X	X	X	X	X	
DLQI	X ^f	X		X			X			X			X		
BSA	X ^f	X	X	X	X	X	X	X	X	X	X	X	X		
mNAPSI	X ^f	X		X			X			X			X		
PSSI	X ^f	X		X			X			X			X		
PGADA	X ^f			X			X			X			X		
SF-36	X ^f			X			X			X			X		

Table 5–1: Schedule of study assessments

Protocol activity	Visit Week ^a PS0011 Baseline	Treatment Period												SFU ^b
		Wk 4	Wk 8	Wk 12	Wk 16	Wk 20	Wk 24	Wk 28	Wk 32	Wk 36	Wk 40	Wk 44	Wk 48/ WD	
HADS	X ^f	X	X	X	X	X	X	X	X	X	X	X	X	X
Concomitant medications	X	X	X	X	X	X	X	X	X	X	X	X	X	X
Adverse events	X	X	X	X	X	X	X	X	X	X	X	X	X	X ^l
IXRS	X	X	X	X	X	X	X	X	X	X	X	X	X	X
Bimekizumab administration ^m	X	X	X	X ^m	X ^m	X ^m	X ^m	X ^m	X ^m	X ^m	X ^m	X ^m	X ^m	

BSA=body surface area; DLQI=Dermatology Life Quality Index; ECG=electrocardiogram; eC-SSRS=electronic Columbia-Suicide Severity Rating Scale; HADS=Hospital Anxiety and Depression Scale; IGA=Investigator’s Global Assessment; IGRA=interferon gamma release assay; IXRS=interactive voice or web response system; mNAPSI=modified Nail Psoriasis Severity Index; PASI=Psoriasis Area and Severity Index; PGADA=Patient’s Global Assessment of Disease Activity; PSSI=Psoriasis Scalp Severity Index; Q4W=every 4 weeks; SF-36=36-item Short Form Health Survey; SFU=Safety Follow-Up; TB=tuberculosis; WD=withdrawal; Wk=week

^a Visit windows of ±3 days from the first dose (Baseline) at all visits except SFU, which has a window of -3 and +7 days from scheduled visit date.

^b The SFU Visit will occur 20 weeks after the last dose of bimekizumab or placebo.

^c Ensure that the informed consent for PS0011 was completed by the subject during the Week 8 or Week 12 Visit of PS0010 (must be done before any study assessments are performed for PS0011).

^d To be performed prior to the first dose of bimekizumab or placebo in PS0011.

^e Includes evaluation of signs and symptoms of active TB and risk for exposure to TB.

^f The noted PS0011 Baseline assessments will be obtained at the Week 12 Visit of PS0010 and do not need to be recorded on the case report form for this study.

^g Vital signs (blood pressure, pulse rate, and temperature) are to be measured prior to blood sampling and prior to dosing, where applicable.

^h Pregnancy testing will be urine testing at all visits except SFU, which will be a serum test.

ⁱ It is recommended that the QuantiFERON TB GOLD test be performed.

^j Ensure that an IGRA test was performed during the Week 8 Visit of PS0010 and the result was negative.

^k All blood samples are to be taken prior to dosing.

^l Including assessment for the development of different forms of psoriasis at the SFU visit.

^m Subjects who received placebo or bimekizumab 64mg, 160mg, or 320mg loading dose + 160mg Q4W in PS0010 must achieve PASI90 response at Week 12 in PS0010 to enter the PS0011 extension study on the same treatment dose. Subjects who do not achieve PASI90 response at Week 12 in PS0010 while receiving placebo or bimekizumab 64mg will be assigned to receive bimekizumab 160mg on entering PS0011. Subjects who do not achieve PASI90 response at Week 12 in PS0010 while receiving bimekizumab 160mg or 320mg loading dose + 160mg will be assigned to receive bimekizumab 320mg Q4W on entering PS0011. Subjects who receive bimekizumab 320mg or 480mg Q4W in PS0010 will be assigned to receive bimekizumab 320mg Q4W on entering PS0011, regardless of their PASI90 response at Week 12 in PS0010. Any subject who does not achieve PASI75 response at Week 12 or later in PS0011 will be withdrawn from study treatment and will return to complete the Early Withdrawal Visit assessments.

[figure not shown]

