8 STUDY PROCEDURES BY VISIT

[Table 5–1](#) (schedule of study assessments) provides a general overview of study assessments. A list of procedures to be completed at each visit is provided in the sections that follow.

- Visit windows of ± 3 days on either side of the scheduled dosing are permitted for all visits other than the SFU Visit (see below); however, the Investigator should try to keep the subjects on the original dosing schedule. The window of ± 3 days is relative to the first dose (Baseline) and applicable for all subsequent visits. Changes to the dosing schedule outside of the 3-day window must be discussed with the Medical Monitor.
- The minimum time between doses should be no less than 24 days and no more than 32 days for Q4W dosing.
- For the SFU Visit (20 weeks after the last dose of bimekizumab or placebo), the visit should occur no more than 3 days prior to the scheduled visit date and within 7 days after the scheduled visit date (-3 days/+7 days).

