8.7 Week 36 (±3 days)

The following procedures or assessments will be performed prior to administration of study drug (if applicable):

- Vital signs (blood pressure, pulse rate, and temperature)
- eC-SSRS
- TB questionnaire
- PASI
- IGA
- DLQI
- BSA
- mNAPSI
- PSSI
- PGADA
- SF-36
- HADS
- Obtain blood sample for:
 - Standard safety laboratory tests (hematology and biochemistry)
- Obtain urine sample for:

-
- Standard safety laboratory tests (urinalysis)
 - Urine pregnancy test for women of childbearing potential
 - Concomitant medications
 - Record AEs
 - Contact the IXRS
 - Study medication administration (after all other visit assessments are completed)

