8.8 Week 48 (±3 days) Study Exit/Early Withdrawal

The following procedures or assessments will be performed:

- Vital signs (blood pressure, pulse rate, and temperature)
- Body weight
- Physical examination
- Record 12-lead ECG
- eC-SSRS
- TB questionnaire
- PASI
- IGA
- DLQI
- BSA
- mNAPSI
- PSSI
- PGADA
- SF-36
- HADS
- Obtain blood samples for:
 - TB test (IGRA; QuantiFERON TB GOLD test is recommended)
 - Standard safety laboratory tests (hematology and biochemistry)
 - Bimekizumab plasma concentration
 - Anti-bimekizumab antibodies
- Obtain urine sample for:
 - Standard safety laboratory tests (urinalysis)
 - Urine pregnancy test for women of childbearing potential

- Concomitant medications
- Record AEs
- Contact the IXRS

8.9 SFU Visit (20 weeks after the last dose of bimekizumab or placebo; -3/+7 days)

The following procedures or assessments will be performed:

- Vital signs (blood pressure, pulse rate, and temperature)
- Body weight
- Physical examination
- eC-SSRS
- Record 12-lead ECG
- PASI
- IGA
- HADS
- Obtain blood samples for:
 - Standard safety laboratory tests (hematology and biochemistry)
 - Serum pregnancy test for women of childbearing potential
 - Bimekizumab plasma concentration
 - Anti-bimekizumab antibodies
- Obtain urine sample for:
 - Standard safety laboratory tests (urinalysis)
- Concomitant medications
- Record AEs (including assessment for development of other forms of psoriasis)
- Contact the IXRS

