8.10 Early Withdrawal Visit

Subjects withdrawing early from the study (see [Section 6.3](#)) will undergo the same assessments as the Week 48 Visit (see [Section 8.4](#)) and will enter the SFU Period.

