7 MEASUREMENTS OF TREATMENT COMPLIANCE

All summaries detailed in this section will be performed on the SS.

Due to the method of administration of the treatments, compliance will be examined in terms of completed injections, where two injections will be considered as one complete treatment administration (ie, one dose).

Treatment compliance will be calculated as:

$$\text{Treatment compliance} = \frac{\text{total number of completed injections}}{\text{total number of expected injections}} \times 100 \quad (3)$$

where the total number of expected injections is derived relative to when the subject finishes treatment. If a subject completes treatment, 24 injections are expected (two at each Q4W). If a subject discontinues early, then the number of expected injections is based on the time of early discontinuation relative to the dosing visits.

A summary of percent treatment compliance categorized as $\leq 80\%$ and $> 80\%$ will be provided by PS0011 treatment group.

A by-subject listing of treatment compliance will be provided.

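### Table 5-1 schedules a 13th dose at Week 48/withdrawal, while the visit procedures, the 64-week maximum and the SAP's 24 injections all allow only 12 doses, ending at Week 44

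*Protocol*

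**What the plan says.** **Table 5-1 (Protocol 5.2).** The row labelled "Bimekizumab administration ^m" is marked at PS0011 Baseline, at every four-weekly visit to Week 44, and in the column shared by Week 48 and withdrawal. The SFU cell is empty. Footnote m is attached to the marks from Week 12 onward and includes this rule: "Any subject who does not achieve PASI75 response at Week 12 or later in PS0011 will be withdrawn from study treatment".

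**Protocol Section 8.** The opening says that Table 5-1 "provides a general overview of study assessments. A list of procedures to be completed at each visit is provided in the sections that follow". Each of Sections 8.1 to 8.7 then ends with a dosing line: "Study medication administration (after all other visit assessments are completed"). The list under "8.8 Week 48 (±3 days) Study Exit/Early Withdrawal" has no such line.

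**Protocol 5.1.1.** "The study duration for each subject is estimated to be up to a maximum of 64 weeks", with the SFU visit 20 weeks after the last dose. SAP 2.3.3 gives the same figures.

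**SAP 7.** Two injections make one dose, and "If a subject completes treatment, 24 injections are expected (two at each Q4W").

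**Protocol 8.10.** Subjects who withdraw early "will undergo the same assessments as the Week 48 Visit (see [Section 8.4](#)) and will enter the SFU Period". Section 8.4 is the Week 12 list; the Week 48 list is Section 8.8.

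**The concern.** The schedule table and the visit-by-visit procedures disagree on whether study drug is given at the last treatment-period visit. A site may well work from the table, so the extra mark acts as a dosing instruction.

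Two groups are affected.

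- **Completers.** A Week 48 dose would be one more than the duration and compliance definitions assume. It would also lengthen by about four weeks the obligations that run for 20 weeks after the last dose: the SFU visit, contraception and the ban on live vaccines.
- **Withdrawing subjects.** Because the column is shared, the mark read literally schedules a dose at the exit visit for subjects withdrawn for lack of PASI75 response, tuberculosis, pregnancy or potential drug-induced liver injury. Footnote m and Protocol 6.3, 6.3.1, 9.1.6 and 9.8.1.4 require treatment to stop in these cases.

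The wrong pointer in Section 8.10 is a smaller slip in the same place. It sends the reader to a list that lacks body weight, physical examination, ECG and the IGRA test, and that does contain a dosing line.

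**Working it through.** **1. Where the last mark falls.** The header has Baseline (1), Weeks 4 to 44 (11), Wk 48/WD (1) and SFU (1), so 14 columns. The dosing row has 3 plain marks (Weeks 0, 4, 8) and 10 marks with footnote m, so 3 + 10 = 13, followed by an empty SFU cell. A row ending at Week 44 would have 3 + 9 = 12.

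A column shift from the PDF conversion is unlikely:

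- In the same part of the table, the HADS, concomitant medication, adverse event and IXRS rows each have 14 marks. The fourteenth adverse event mark carries footnote l, which concerns the SFU visit, so the right-hand end is aligned.
- The first mark with footnote m is the fourth, at Week 12, which is where that footnote's withdrawal rule begins.
- In the first part of the table, the BSA row also has 13 marks and an empty SFU cell. BSA is listed in Section 8.8 and not in Section 8.9 (SFU), as that alignment requires.

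**2. Dosing visits in Section 8.**

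| Section | Visits | Dosing visits |
|---|---|---|
| 8.1 | Baseline | 1 |
| 8.2 | Week 4 | 1 |
| 8.3 | Weeks 8, 16, 32, 40 | 4 |
| 8.4 | Week 12 | 1 |
| 8.5 | Weeks 20, 28, 44 | 3 |
| 8.6 | Week 24 | 1 |
| 8.7 | Week 36 | 1 |
| 8.8 | Week 48/withdrawal | 0 |

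The total is 12. The introductory sentences of 8.1 to 8.7 place the assessments before dosing. That wording is absent from 8.8, as it is from the SFU list, so the missing dosing line does not look like an oversight.

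**3. Reproducing the plan's own figures.** Doses = number of four-weekly visits from Week 0 to the last dose; injections = 2 × doses; maximum duration = week of last dose + 20; SAP 8.1.2 exposure = days from first to last dose + 28, capped at the Week 48 visit (48 × 7 = 336 days).

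| Quantity | Last dose Week 44 | Last dose Week 48 | Plan states |
|---|---|---|---|
| Doses | 12 | 13 | – |
| Injections | 24 | 26 | 24 |
| Maximum duration (weeks) | 44 + 20 = 64 | 48 + 20 = 68 | 64 |
| Exposure before cap (days) | 308 + 28 = 336 | 336 + 28 = 364 | cap at 336 |

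Both stated figures reproduce exactly with a Week 44 last dose, and neither does with Week 48. The exposure formula also fits Week 44 without needing the cap; a Week 48 dose would be credited with no exposure time at all.

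**4. Size of the discrepancy for a completer.**

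- Cumulative dose: 13/12 = 1.083, or +8.3%. At 320 mg Q4W this is 13 × 320 = 4160 mg against 12 × 320 = 3840 mg.
- Compliance: 26/24 = 108%, still in the SAP's >80% category.
- Time in study: 68 − 64 = 4 weeks longer.

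**5. Effect on the primary safety analysis.** Protocol 14.3 and 14.3.1 end both the TEAE window and the exposure at risk 140 days after the actual last dose. An extra Week 48 dose moves both by the same 28 days (44 × 7 + 140 = 448 against 48 × 7 + 140 = 476), so numerator and denominator stay matched. SAP 8.1.3 has exceptions for death, loss to follow-up and data cutoff, which end the exposure at last contact or cutoff; they do not change this conclusion.

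**The case against.** The strongest counter-evidence is that the table is not quite alone. Sections 1 and 5.1 of the protocol describe four-weekly visits for assessments and dosing running through Week 48, and SAP 8.2.6 speaks of an administration period of 48 weeks. Section 8 describes the table as an overview and the visit lists as the procedures to complete, but it does not state in so many words which prevails. This stands in part. The wording is ambiguous, and giving precedence to Section 8.8 is an inference, though a natural one. The phrases can describe the visits or the treatment period; read as a Week 48 dose, they cannot be squared with 64 weeks or with 24 injections. IXRS contact at Week 48 does not imply dosing either, since IXRS is also contacted at the SFU visit.

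The second objection is that the harm is small. The stop rules are explicit, Section 8.10 prescribes assessments only, and IXRS controls allocation, so a site would have to override a specific rule on the strength of one mark in a shared column. For completers, the follow-up periods move with the last dose. This limits the harm, and the risk at withdrawal visits is low, but the conflicting instruction remains. The documents do not say whether IXRS would release a kit at that visit.

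The Section 8.10 pointer is rightly called minor. Its wording names the Week 48 Visit, and Table 5-1 marks all four assessments missing from Section 8.4. Section 9.8.1.1 separately requires the IGRA, and Section 9.8 ties body weight, ECG and physical examination to the table.

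**Conclusion.** The concern holds: the dosing mark under Wk 48/WD is wrong as written and should be fixed. The table gives 13 doses; Sections 8.1 to 8.8, the 64-week maximum and the SAP's compliance definition give 12. The consequence is at most one unintended dose per subject, at a dose level the subject was already receiving. The figures for duration and compliance concern completers only. For withdrawing subjects the conflict is with Section 8.8, footnote m and the stop rules. No planned estimate is biased.

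The conclusion rests on two readings: that the extracted table is correctly aligned, which several other rows support, and that the visit lists take precedence over the overview table, which Section 8 implies and the duration and injection counts corroborate.

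**What to change.** 1. Delete the dosing mark in the Wk 48/WD column of Table 5-1.
2. In Section 8.10, change the cross-reference from Section 8.4 to Section 8.8.
3. At the same time, preferably, state in Sections 1 and 5.1 that visits run through Week 48 and that the last dose is at Week 44.

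The cost is an administrative clarification of the protocol: one table cell, one cross-reference and, if step 3 is taken up, one sentence in each of two sections. The SAP already assumes 12 doses and needs no change.

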5.3 Schematic diagram

A study schematic diagram of PS0011 is presented in [Figure 5-1](#).

This document cannot be used to support any marketing authorization application and any extensions or variations thereof.

REDACTED COPY

Figure 5–1: Schematic diagram

PASI=Psoriasis Area and Severity Index; Q4W=every 4 weeks; SFU=Safety Follow-Up

^a Subjects who received placebo or bimekizumab 64mg, 160mg, or 320mg loading dose + 160mg Q4W in PS0010 must achieve PASI90 response at Week 12 in PS0010 to enter the PS0011 extension study on the same treatment dose. Subjects who do not achieve PASI90 response at Week 12 in PS0010 while receiving

-
- placebo or bimekizumab 64mg will be assigned to receive bimekizumab 160mg on entering PS0011. Subjects who do not achieve PASI90 response at Week 12 in PS0010 while receiving bimekizumab 160mg or 320mg loading dose + 160mg will be assigned to receive bimekizumab 320mg Q4W on entering PS0011.
- ^b Subjects who receive bimekizumab 320mg or 480mg Q4W in PS0010 will be assigned to receive bimekizumab 320mg Q4W on entering PS0011, regardless of their PASI90 response at Week 12 in PS0010.
- ^c Any subject who does not achieve PASI75 response at Week 12 or later in PS0011 will be withdrawn from study treatment and will return to complete the Early Withdrawal Visit assessments.

5.4 Rationale for study design and selection of dose

PS0011 is a 48-week, double-blind, placebo-controlled, parallel-group extension study for eligible subjects who complete PS0010, a Phase 2b, randomized, double-blind, placebo-controlled, parallel-group, dose-ranging study in adult subjects with moderate to severe chronic plaque psoriasis. Because some PS0010 subjects may have severe disease, the treatment in PS0011 provides more time to respond to a potentially efficacious treatment. PS0011 also provides an opportunity for nonresponding PS0010 placebo subjects to receive bimekizumab. This study will allow the collection of further data on the long-term safety, tolerability, and efficacy of bimekizumab in this subject population.

The PS0011 design (Figure 5–1) allows PASI90 responders in PS0010 to continue their dose in PS0011, thus permitting these subjects to remain on the dose that resulted in this response after 12 weeks of initial treatment in PS0010. It also provides an opportunity for an increased dose among PS0010 nonresponders (ie, <PASI90). PASI90 was selected as the response criterion in PS0010 to ensure that a sufficiently high efficacy response was achieved. This type of dose escalation for those who do not achieve a desired response after 12 weeks is common in clinical practice.

Regardless of PASI90 response at Week 12 of PS0010, subjects who received the 2 highest doses of bimekizumab (320mg and 480mg Q4W) in PS0010 will begin PS0011 on the 320mg Q4W dose. For those subjects who do achieve PASI90 response, this will allow a continuation of the PS0010 dose for subjects initially receiving 320mg Q4W and a dose down for subjects originally randomized to the 480mg Q4W dose. Because bimekizumab 480mg Q4W is the highest dose evaluated in PS0010 and because it requires 3 injections, it will be of interest to evaluate whether these subjects can maintain response in PS0011 with the lower 320mg dose, allowing the blind to be maintained with the use of only 2 injections at each study administration visit.

To protect against the possibility of exposing subjects to an ineffective treatment for extended periods of time, subjects across all treatment groups who have not achieved PASI75 response at Week 12 or later in PS0011 will be withdrawn from study treatment. Because this withdrawal decision is based strictly on the PASI response and not on the original study treatment, it can be done in such a way that will not unblind subjects or Investigators.
